| Adverse event assessment | ✓ | ✓ | ✓ | ✓ | ✓ | ✓ | ✓ | ✓ | ✓ | ✓ | ✓ | ✓ | ✓ | ✓ |
| Investigator Assessments (PGA) | | ✓ | ✓ | ✓ | ✓ | ✓ | ✓ | ✓ | ✓ | ✓ | ✓ | ✓ | ✓ | |
| Investigator Assessments (TJC, SJC, BSA-P50 ^b) | ✓ | ✓ | ✓ | ✓ | ✓ | ✓ | ✓ | ✓ | ✓ | ✓ | ✓ | ✓ | ✓ | |
| Investigator Assessments (LDI, LEI, SPARCC) | | ✓ | | | | ✓ | ✓ | | | ✓ | | ✓ | ✓ | |
| Investigator Assessments (PAS) ^a | | ✓ | ✓ | ✓ | ✓ | ✓ | ✓ | ✓ | ✓ | ✓ | ✓ | ✓ | ✓ | |
| Investigator Assessments (Psoriatic Spondylitis Question) | | ✓ | | | | | | | | | | | | |
| Bilateral radiographs of hands and feet ^c | ✓ | | | | | | | | | | | | | |
| Central Laboratory Test – Serum pregnancy | ✓ | | | | | | | | | | | | | |
| Local urine pregnancy test | | ✓ | ✓ | ✓ | ✓ | ✓ | ✓ | ✓ | ✓ | ✓ | ✓ | ✓ | ✓ | |

| Activity | Screening | BASELINE | W4 | W8 | W12 | W16 | W24 | W28 | W32 | W36 | W40 | W52 to W208 (Every 12 Weeks) | Completion or PD (12 Weeks Post Last Dose) | F/U Call (20 Weeks Post Last Dose) |
|--|-------------|----------|-----|-----|-----|------|------|------|------|------|------|------------------------------|--|------------------------------------|
| | D-35 to D-1 | D1 | D28 | D56 | D84 | D112 | D168 | D196 | D224 | D252 | D280 | D364 to D1456 | D1540 | D1596 |
| Central Laboratory Tests – hsCRP, Clinical Chemistry, Hematology | ✓ | ✓ | ✓ | ✓ | ✓ | ✓ | ✓ | ✓ | ✓ | ✓ | ✓ | ✓ | ✓ | |
| Central Laboratory Tests – Total Cholesterol, HDL-C, LDL-C, Triglyceride | | ✓ | | | | | | | | | | | | |
| Central Laboratory Tests – TB screen (QuantiferON-TB Gold test [or IGRA equivalent] and/or local purified protein derivative [PPD] skin test) ^d | ✓ | | | | | | | | | | | ✓ | ✓ | |
| Central Laboratory Tests – HIV Screening, Hepatitis B and C Screening, Rheumatoid Factor, Anti-CCP antibodies, Urinalysis, FSH | ✓ | | | | | | | | | | | | | |
| Blood samples for Risanalizumab PK assay ^e | | | | | | | | ✓ | | | | ✓ | | |
| Blood samples for Risanalizumab ADA assay and neutralizing antibody (nAb) assay ^e | | ✓ | | | | | | ✓ | | | | ✓ | | |
| Calculation of TIC/SIC responses | | | | | ✓ | ✓ | | | ✓ | ✓ | ✓ | ✓ | | |
| Anaphylaxis Monitoring ^f | | ✓ | ✓ | | | ✓ | ✓ | ✓ | | | ✓ | ✓ | | |

| Activity | Screening | BASELINE | W4 | W8 | W12 | W16 | W24 | W28 | W32 | W36 | W40 | W52 to W208 (Every 12 Weeks) | Completion or PD (12 Weeks Post Last Dose) | F/U Call (20 Weeks Post Last Dose) |

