3.12 Clinical Laboratory Tests

A certified laboratory will be utilized to process and provide results for the clinical laboratory tests. Laboratory reference ranges will be obtained prior to the initiation of the study. The Baseline (Day 1) laboratory test results for clinical assessment for a particular test will be defined as the last measurement prior to the initial dose of study drug.

Instructions regarding the collection, processing, and shipping of these samples will be provided by the central laboratory.

If a laboratory test value is outside the reference range and the investigator considers the laboratory result to be clinically significant, the investigator will:

- repeat the test to verify the out-of-range value;
- follow the out-of-range value to a satisfactory clinical resolution; or
- discontinue the subject from the study or require the subject to receive treatment; in this case, the laboratory result will be recorded as an adverse event.

| Clinical Laboratory Tests | | |
|---|--|--|
| Hematology | Clinical Chemistry | Other Tests |
| Hematocrit Hemoglobin Red Blood Cell (RBC) count White Blood Cell (WBC) count Neutrophils Bands, if detected Lymphocytes Monocytes Basophils Eosinophils Platelet count Coagulation: International Normalized Ratio (INR) ^a | Blood Urea Nitrogen (BUN) Creatinine Total bilirubin Direct and indirect bilirubin ^c Alanine transaminase (SGPT/ALT) Aspartate transaminase (SGOT/AST) Gamma-glutamyl transferase (GGT) Alkaline phosphatase Sodium Potassium Calcium Cholesterol ^d Total protein Glucose Triglycerides ^d LDL ^d HDL ^d Albumin Chloride Bicarbonate/CO ² Estimated glomerular filtration rate (eGFR) Chronic Kidney Disease Epidemiology Collaboration (CKD-EPI) | Hepatitis B surface antigen (HBs Ag, qualitative) ^b Hepatitis B core antibody (HBc Ab)/anti-HBc (qualitative) ^b HBs Ab/anti-HBs (qualitative) ^b Hepatitis B Virus DNA (reflex, quantitative) ^b Hepatitis C Antibodies (qualitative) ^b Hepatitis C Virus RNA (reflex, quantitative) ^b HIV-1 and HIV-2 Antibody (qualitative) ^b Human Chorionic Gonadotropin (hCG) ^{b,e} for females (quantitative) Rheumatoid Factor ^b Anti-CCP antibodies ^b hsCRP FSH ^{b,f} TB screen (QuantiFERON-TB Gold Test) Anaphylaxis Testing^g Tryptase ^g Histamine ^g Serum risankizumab concentrations ^g ADA/nAb sample ^g Local Labs TB screen (PPD Skin Test), if needed Urine hCG for females ^e |
| Urinalysis^b | | |

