A pregnant or breastfeeding female will not be eligible for participation or continuation in this study.

Urine Pregnancy Test

Additional urine pregnancy tests for female subjects of childbearing potential will be performed at visits indicated in Section 2.1. More frequent pregnancy tests will be performed throughout the study if required per local/country requirements.

If the urine pregnancy test (which is performed at the site) is negative, begin or continue dosing. If urine pregnancy test is positive, withhold dosing and perform a serum pregnancy test. Pregnant subjects must discontinue from the study.

Chemistry

Blood samples at Baseline will be collected following a minimum 8-hour fast. If a subject is not able to fast due to unforeseen circumstances, the nonfasting status will be recorded in study source documentation and lab requisition. Subjects are not required to fast before laboratory assessments at other time points.

[figure not shown]
Urinalysis

Dipstick urinalysis will be completed by the central laboratory at the Screening Visit. Specified abnormal macroscopic urinalyses dipstick results will be followed up with a microscopic analysis at the central laboratory.

Hepatitis B and C Testing

All subjects will be tested for the presence of the hepatitis B virus (HBV) and hepatitis C virus (HCV) at Screening. Subjects with hepatitis B (HBs Ag positive [+] or detected sensitivity on the HBV DNA PCR qualitative test) or hepatitis C (HCV RNA detectable in any subject with anti-HCV Ab) will be excluded. Subjects who have been vaccinated against hepatitis B and are HBs Ab positive may be enrolled. If Hepatitis B Surface Antigen is negative but Hepatitis B Core Antibodies total is positive, Hepatitis B Virus DNA will be quantified. If Hepatitis B Virus DNA level is undetectable at Screening, the subject can participate in this trial. If Hepatitis C Virus Antibodies is positive, Hepatitis C Virus RNA will be quantified. If Hepatitis C RNA level is undetectable at Screening, the subject can participate in this trial.

Figure 1. Interpretation and Management of HBV Serologic Test Results

* A positive test result for HBs Ab is expected for subjects who have had a HBV vaccination. For subjects without a history of HBV vaccination (and where mandated by local requirements), a positive result for HBs Ab requires HBV DNA PCR testing.

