9.3.2.1 Assessment of Mean Change from Baseline in Clinical Laboratory Variables

Analyses of key continuous hematology and chemistry variables which are measured longitudinally will be performed by visits and by treatment group. For each parameter at each visit, the following summary statistics will be presented for each treatment group: sample size, mean, standard deviation, minimum, median and maximum.

An ANOVA model with treatment as a factor will be used to compare change from baseline between different treatment groups for selected laboratory parameters. Mean difference from placebo and associated 95% CIs will be presented. The analysis applies to the following laboratory parameters of clinical interest

- Hematology parameters: WBC, neutrophils, lymphocytes, RBC, hematocrit, hemoglobin, platelets count.
- Chemistry parameters: total bilirubin, GGT, ALP, SGOT/AST, SGPT/ALT, glucose, creatinine, potassium, sodium, calcium.

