9.3.2.3 Assessment of Potentially Clinically Significant Laboratory Values

Laboratory abnormalities will be evaluated based on PCS criteria ([Appendix C](#)) (defined as a lab value \geq grade 3 NCI CTCAE v4.03 severity). For each laboratory PCS criterion, the number and percentage of subjects who have at least one post-baseline on-treatment value meeting the criteria will be summarized by actual treatment group. A listing of all observations collected will be generated for subjects who had at least one post-baseline observation meeting pre-defined criteria for potentially clinically significant values. A post baseline value must be more extreme than the baseline value to be considered a potentially clinically significant finding.

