9.3.3.2 Assessment of Potentially Clinically Significant Laboratory Values

Long-term laboratory data will also be summarized based on the number and percentage of subjects meeting the criteria for potentially clinically significant (PCS) laboratory values for the Any Risankizumab 150 mg group.

The baseline value will be determined by the last non-missing measurement recorded on or before the date of the first dose of risankizumab 150 mg. For a subject who started on placebo and switched to risankizumab 150 mg at Week 24, lab values under risankizumab 150 mg exposure would be evaluated against the baseline value defined as above.

A listing of all subjects with any laboratory determination meeting CTCAE criteria of Grade 3 or higher will be provided by Grade. For each of these subjects, the whole course of the respective parameter will be listed.

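### Baseline glucose is fasted and later glucose need not be, so within-arm and long-term changes carry an upward bias of unknown size, while the randomized Period 1 difference does not.

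*Protocol*

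**What the plan says.** Operations Manual 3.12 sets the sampling condition for chemistry. At Baseline, "Blood samples at Baseline will be collected following a minimum 8-hour fast". If a subject cannot fast, "the nonfasting status will be recorded in study source documentation and lab requisition". For all other visits, "Subjects are not required to fast before laboratory assessments at other time points". No recording of fasting status is described for those visits.

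The baseline laboratory value "will be defined as the last measurement prior to the initial dose of study drug", and SAP 8.1 defines baseline in the same way. That is normally the fasted Day 1 sample.

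Glucose belongs to the chemistry panel, which the Activity Schedule (Protocol Appendix D, row "Central Laboratory Tests – hsCRP, Clinical Chemistry, Hematology") ticks at Screening, Baseline and every later clinic visit. In the Operations Manual 3.12 test table, only the lipids carry the footnote limiting them to Baseline. Glucose does not.

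SAP 9.3.2.1 lists the chemistry variables for the Period 1 comparison of change from baseline: "Chemistry parameters: total bilirubin, GGT, ALP, SGOT/AST, SGPT/ALT, glucose, creatinine, potassium, sodium, calcium". The model is an ANOVA with treatment as the only factor. SAP 9.3 adds that the mean change, its standard error and a 95% confidence interval are shown within each arm as well as between arms. SAP 9.3.3.1, for long-term data, has mean change from baseline in its heading. Its text promises descriptive statistics by visit and treatment sequence for specified variables.

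For potentially clinically significant (PCS) values, SAP 9.3.2.3 states: "A post baseline value must be more extreme than the baseline value to be considered a potentially clinically significant finding". The high glucose limit is 13.9 mmol/L (SAP Appendix C, Table C-2). For the long-term PCS analysis, SAP 9.3.3.2 states: "The baseline value will be determined by the last non-missing measurement recorded on or before the date of the first dose of risankizumab 150 mg".

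**The concern.** A change from baseline can be read as a change in the subject only if both values are taken under the same conditions. Here a fasted value is subtracted from values with no fasting requirement. If unfasted glucose is on average higher than fasted glucose, the mean change moves upward in both arms with no drug effect at all. The SAP nevertheless puts a confidence interval around that within-arm change.

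At stake is the reading of one safety laboratory variable. A table showing glucose above baseline on risankizumab, in Period 1 or over open-label dosing to Week 208, could be taken for a metabolic signal when part or all of it reflects the sampling condition. Because fasting status is not recorded after Baseline under the plan as written, it could not be corrected for afterwards.

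**Working it through.** The plan states no glucose figure, so there is none to reproduce.

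**Inputs from the documents.** 210 subjects per arm, 1:1 (Protocol 7.3). Fast at Baseline, with exceptions allowed; no fast required later (Operations Manual 3.12).

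**Inputs that are assumptions.** None of these is in the documents:
- d, mean unfasted minus fasted glucose: 0.3 to 1.0 mmol/L
- f_later, share of later samples that are unfasted: 0.25 to 1.0
- f_base, share of Baseline samples that are unfasted: 0 to 0.05
- SD of change: 1.0 to 2.0 mmol/L

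**Formulas.** Artefact in an arm's mean change = d × (f_later − f_base). Within-arm 95% CI = artefact ± 1.96 × SD/√210. For SD 1.5, the standard error is 1.5/√210 = 0.104 and the half-width is 1.96 × 0.104 = 0.20.

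| d | f_later | f_base | Artefact (mmol/L) | 95% CI, SD 1.5, no drug effect |
|---|---|---|---|---|
| 0.3 | 0.25 | 0.05 | 0.3 × 0.20 = 0.06 | −0.14 to 0.26 |
| 0.3 | 0.25 | 0 | 0.3 × 0.25 = 0.075 | −0.13 to 0.28 |
| 0.3 | 0.50 | 0 | 0.3 × 0.50 = 0.15 | −0.05 to 0.35 |
| 0.6 | 0.75 | 0 | 0.6 × 0.75 = 0.45 | 0.25 to 0.65 |
| 1.0 | 1.0 | 0 | 1.0 × 1.0 = 1.00 | 0.80 to 1.20 |

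The artefact is positive whenever d > 0 and more subjects are unfasted later than at Baseline. It is zero if the two shares are equal.

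**Between arms.** With the same d and f in both arms the artefact cancels in expectation. A simulation of 4,000 trials per setting (210 per arm, SD 1.5, all Baseline samples fasted, no drug effect) gave:

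| d, f_later | Mean between-arm difference (mmol/L) | Between-arm rejection rate | Placebo within-arm CI wholly above 0 |
|---|---|---|---|
| 0.3, 0.50 | 0.002 | 5.5% | 31% |
| 0.6, 0.75 | −0.001 | 4.7% | 99% |
| 1.0, 1.0 | −0.002 | 4.5% | 100% |

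The randomized comparison holds its level; the within-arm interval does not.

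**PCS counts.** A later glucose above 13.9 mmol/L exceeds any baseline at or below 13.9 automatically. The rule about being more extreme than baseline can therefore change a classification only for a subject whose baseline is already above 13.9. The same reasoning applies at the low limit of 2.2 mmol/L.

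**The case against.** The strongest reply is that the analysis that matters is already protected. SAP 9.3 introduces change from baseline as a means of comparing risankizumab with placebo in Period 1, and that comparison is unbiased. Protocol 7.4 calls laboratory changes descriptive. Glucose is not an area of safety interest (SAP Appendix B) and is not in the toxicity-grade shift tables (SAP 9.3.2.2). All of this stands and limits the severity. It does not remove the within-arm intervals that SAP 9.3 also plans.

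Four stronger readings are tempting, and the documents do not support them.

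- *A large rise is certain.* Taking every Baseline sample as fasted and every later one as unfasted, a reader might assume a shift of 0.5 to 1.5 mmol/L and an SD of 1.5 to 2.0, and find the within-arm change 3.6 to 14.5 standard errors above zero (0.5/0.138 to 1.5/0.104). But a later fast is not forbidden, and unfasted Baseline samples are allowed. With partial fasting the shift can be 0.075/0.104 = 0.7 standard errors.
- *Four years of uncontrolled false signal.* SAP 9.3.3.1 mentions change only in its heading, does not name glucose, and plans no interval or test. Long-term summaries cover both periods and are shown by sequence (SAP 9.1). The placebo-to-risankizumab sequence would therefore show the shift at its placebo visits, before any active drug. That exposes the artefact in part.
- *Distorted PCS counts.* In the long-term analysis the original risankizumab arm keeps a fasted Day 1 reference, while placebo switchers normally have a Week 24 reference with no required fast. The inconsistency is real, but it matters only for a baseline already beyond a limit. The results are also pooled in one Any Risankizumab group, and SAP 9.3.3.2 does not restate the rule about being more extreme than baseline.
- *The Screening value is a clean replacement baseline.* It would depart from the last-value-before-dose definition in both documents, and it can precede stabilisation of oral corticosteroids.

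**Conclusion.** The point holds as a minor one. Following the plan as written, within-arm and long-term glucose changes mix sampling condition with any change in the subject, and the mixing runs upward in all groups. The direction rests on two assumptions: unfasted glucose averages higher than fasted, and more subjects are unfasted later than at Baseline. The size, about 0.06 to 1.0 mmol/L per arm, rests wholly on the assumed ranges above. At the low end nobody would notice it; in the middle of the range the within-arm interval excludes zero with no drug effect. The Period 1 difference from placebo remains interpretable, provided that fasting habits at later visits do not differ by arm, which blinding makes reasonable.

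**What to change.** In SAP 9.3, 9.3.2.1 and 9.3.3.1, make an exception for glucose:

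- report the Period 1 between-arm difference in change, and absolute values by visit;
- drop the within-arm change and the long-term change from the fasted Baseline;
- footnote the glucose tables to say that Baseline was collected fasted and that later visits did not require a fast.

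Optionally, add a sensitivity summary with the Screening glucose as reference. Screening chemistry is scheduled for all subjects and, like the later visits, requires no fast. Its downside is timing. It can be up to 35 days before dosing, whereas eligibility criterion 31 asks for stable oral corticosteroids for only 1 week before Baseline and Protocol 5.4 refers to 4 weeks (28 days). A draw at Day −35 precedes both. It should therefore supplement the defined baseline and not replace it.

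The cost is a few sentences in the SAP and a small change to the table programs. No new samples, visits or data are needed. What is lost is a within-arm summary that could not be interpreted anyway.

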3.13 Drug Concentration and Anti-Drug Antibody Measurements

Pharmacokinetic, ADA, and nAb samples should be collected within 60 minutes prior to the dose at dosing visits.

Collection of Blood Samples for Risankizumab Analysis, ADA Assay, and nAb Assay

Blood samples for analysis of risankizumab serum concentrations, ADA assay, and nAb assay will be collected during the treatment period on the study days and time points specified in the protocol. Samples will be collected by venipuncture into appropriately labeled, evacuated serum collection tubes. The time that each blood sample (PK and ADA/nAb) is collected will be recorded to the nearest minute.

Measurement Methods

Serum concentrations of risankizumab and ADA and nAb assessments will be done using validated methods at or under the supervision of the Bioanalysis Department at AbbVie. The presence of ADA to risankizumab will be assessed via a tiered approach with an electrochemiluminescence assay using screening, confirmatory, and titration analyses. Samples that are confirmed positive may be further characterized in a validated nAb assay. Any additional analytes may be analyzed using nonvalidated methods. Serum samples collected for risankizumab PK and ADA analysis may be used for future assay development or validation activities. Risankizumab nAb samples upon request may be used for the analysis of neutralizing ADAs.

Disposition of Samples

The frozen serum samples for risankizumab analysis, ADA and nAb assays will be packed in dry ice sufficient to last during transportation and shipped from the study site to the central lab according to instructions from AbbVie.

3.14 Out of Window Visits Due to COVID-19 Pandemic

[figure not shown]
If a visit can be performed onsite but OOW, consult with the sponsor to determine if the OOW visit is permitted.

Regardless of whether an onsite OOW visit can occur, a phone call from the site to the enrolled subject should be conducted as close to the date of the study visit as possible to query for any AEs and to review concomitant medications.

4 SAFETY MANUAL

4.1 Methods and Timing of Safety Assessment

All serious adverse events (SAEs) as well as protocol-related nonserious AEs (e.g., bruising related to blood draw) will be collected from the time the subject signed the study-specific informed consent until study drug administration. From the time of study drug administration until 140 days (20 weeks) following discontinuation of study treatment has elapsed, all AEs and SAEs will be collected, whether solicited or spontaneously reported by the subject.

4.2 Definition of Adverse Event

An AE can result from use of the drug as stipulated in the protocol or labeling, as well as from accidental or intentional overdose, drug abuse, or drug withdrawal. Any worsening of a pre-existing condition or illness is considered an AE. Worsening in severity of a reported AE should be reported as a new AE. Laboratory abnormalities and changes in vital signs are considered to be AEs only if they result in discontinuation from the study, necessitate therapeutic medical intervention, meets protocol specific criteria (see Section 6.2 in the **Protocol** regarding toxicity management), and/or if the investigator considers them to be AEs.

An elective surgery/procedure scheduled to occur during a study will not be considered an AE if the surgery/procedure is being performed for a pre-existing condition and the surgery/procedure has been pre-planned prior to study entry. However, if the pre-existing condition deteriorates unexpectedly during the study (e.g., surgery performed earlier than planned), then the deterioration of the condition for which the elective surgery/procedure is being done will be considered an AE.

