7.4 Statistical Analyses for Safety

Safety analyses will be carried out using the Safety Analysis Set. There will be two sets of planned safety analysis: safety analysis by Week 24, and long-term safety analysis. Safety will be assessed by AEs, physical examinations, laboratory assessments, and vital signs. Frequency tables and lists of subjects with treatment emergent AEs by preferred term as in the Medical Dictionary for Regulatory Activities (MedDRA), by system organ class and preferred term, by severity, and by relationship to the study drug as assessed by the Investigator will be provided. The changes from Baseline in vital signs, physical examination results, and clinical laboratory values will be analyzed in a descriptive manner. Shift of laboratory values from Baseline to defined time points will be tabulated.

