4.6 Recording Data and Analyses of Safety Findings

Adverse events will be coded using the Medical Dictionary for Regulatory Activities (MedDRA). The number and percentage of subjects with treatment-emergent AEs (i.e., any event that begins or worsens in severity after initiation of study drug through 140 days post-study drug dosing) will be tabulated by primary MedDRA System Organ Class (SOC) and preferred term (PT). The tabulation of the number of subjects with treatment-emergent AEs by severity grade and relationship to study drug also will be provided. Subjects reporting more than one AE for a given MedDRA preferred term will be counted only once for that term using the most severe grade for the severity grade table and the most related for the relationship to study drug tables. Subjects reporting more than one type of event within a SOC will be counted only once for that SOC.

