For EAER calculation, the numerator will be the total number of AEs reported for the event (i.e., a subject can contribute more than one event to the numerator) and the denominator will be the total exposure time among subjects under the treatment group. The number of AEs reported (numerator), the total number of years of study drug exposure (denominator, calculated as total number of days exposed to study drug (i.e., last dose date – first dose date + 140 days) for all treated subjects divided by 365.25), and the exposure-adjusted AE event rate per 100 patient-years calculated as $(\text{[numerator (number of AEs)/denominator]}) \cdot 100$ will be presented for each treatment group.

All continuous laboratory parameters and vital signs variables at each visit will be summarized by actual treatment group sequence defined as follows.

1. Placebo → Risankizumab 150 mg
2. Risankizumab 150 mg → Risankizumab 150 mg

Frequency tables and listings of subjects meeting criteria for potentially clinically significant vital sign values and for potentially clinically significant laboratory values will be provided for Any Risankizumab group by actual treatment received at the time of event. Missing safety data will not be imputed.

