9.2.2 Analysis of Adverse Events for Long-Term

Long-term adverse event rates will be analyzed using event rates adjusted by cumulative exposure and will be based on the actual treatment received at the time of AE occurrence for the Any risankizumab 150 mg group. This includes AEs occurred under risankizumab 150 mg exposure from subjects starting on risankizumab 150 mg and subjects switching from placebo to risankizumab 150 mg.

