9.2.2.1 Overview of Adverse Events Rates per 100 Patient-Years of Study Drug Exposure

An overview of TEAE per 100 patient-years of study exposure will be presented for the AE categories defined in Section 9.2.1.1.

An overview of ASI per 100 patient-years of study exposure will be presented similarly.

9.2.2.2 Adverse Events Rates per 100 Patient-Years of Study Drug Exposure by SOC and PT

The TEAE rate per 100 patient-years of exposure will be calculated overall, for each SOC and PT, for the same AEs defined in Section 9.2.1 and reported for Any risankizumab 150 mg group.

9.2.2.3 Serious Adverse Events (Including Deaths) and Adverse Events Leading to Study Drug Discontinuation

SAEs (including deaths) and AEs leading to study drug discontinuation will be listed in tables, besides summary by SOC and PT covered in Section 9.2.2.2.

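### SAP 9.2.2 specifies long-term adverse events only as record-based rates and omits the subject counts that the Operations Manual plans, so repeat and worsening records cannot be told from more subjects affected

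*Protocol*

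**What the plan says.** **Recording.** Operations Manual 4.2 (Protocol Appendix F) states: "Worsening in severity of a reported AE should be reported as a new AE".

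**Rate.** For the exposure-adjusted event rate (EAER), SAP 9.1 says "the numerator will be the total number of AEs reported for the event" and adds that "a subject can contribute more than one event to the numerator". A subject's exposure is "last dose date – first dose date + 140 days"; days are summed and divided by 365.25.

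**Long-term output in the SAP.** SAP 9.2.2 opens: "Long-term adverse event rates will be analyzed using event rates adjusted by cumulative exposure". Its parts are:
- 9.2.2.1: "An overview of TEAE per 100 patient-years of study exposure will be presented for the AE categories defined in Section 9.2.1.1", and a similar overview for events of safety interest.
- 9.2.2.2: the same kind of rate by system organ class (SOC) and preferred term (PT).
- 9.2.2.3: listings of serious events, deaths and events leading to discontinuation.
- 9.2.2.4: rates for events of safety interest. It also has summaries by SOC and PT whose statistic is not stated, under a section title that speaks of rates.

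**Subject counts planned elsewhere.** Operations Manual 4.6 plans the number and percentage of subjects with treatment-emergent events, from first dose to 140 days after dosing, by SOC and PT. It adds: "Subjects reporting more than one AE for a given MedDRA preferred term will be counted only once for that term". Protocol 7.4 names a Week 24 and a long-term safety analysis and then plans "Frequency tables and lists of subjects with treatment emergent AEs by preferred term".

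**The concern.** Two features combine. First, the numerator is a count of records, and the recording rule creates a new record at each worsening. The rate therefore rises with stepwise worsening even when no new episode occurs and no further subject is affected. Second, SAP 9.2.2 sets nothing beside the rate that is immune to this. In Period 1 the SAP also gives event rates, but next to the number and percentage of subjects. In the long-term analysis the rate stands alone.

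Long-term safety is a stated secondary objective (Protocol 3.1), and the long-term period holds most of the risankizumab exposure. A reader of the tables as specified could not say how many subjects had a given non-serious event that did not lead to discontinuation, such as most injection-site reactions.

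**Working it through.** The plan states no expected long-term event rate and no frequency of worsening, so there is no figure to reproduce. The check applies the SAP 9.1 formula.

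**1. Maximum planned exposure.** Inputs: 210 subjects per arm; last dose at Week 208 (day 1,456); switch from placebo at Week 24 (day 168); 140 days added. Assumption: no dropout.
- Randomized to risankizumab: (1,456 + 140)/365.25 = 4.37 years each.
- Placebo, after the switch: (1,456 − 168 + 140)/365.25 = 3.91 years each.
- Total: 210 × (1,596 + 1,428)/365.25 = 1,738.6 patient-years.
- Risankizumab exposure within Period 1: 210 × 168/365.25 = 96.6 patient-years, or 96.6/1,738.6 = 5.6%. About 94% lies outside the period for which the SAP specifies subject-level event tables.

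**2. How a worsening enters.** An event that goes from mild to moderate to severe yields three records. It adds 100 × 3/1,738.6 = 0.17 per 100 patient-years, exactly what three subjects with one event each would add.

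**3. Range of inflation, by assumption only.** If a share w of episodes worsens once and a share v twice, the ratio of records to episodes is 1 + w + 2v, whatever the exposure. Take 1,000 episodes for illustration, which is 100 × 1,000/1,738.6 = 57.5 per 100 patient-years by episode. By record:
- w = 5%, v = 0: factor 1.05, rate 60.4
- w = 10%, v = 2%: factor 1.14, rate 65.6
- w = 20%, v = 5%: factor 1.30, rate 74.8
- w = 30%, v = 10%: factor 1.50, rate 86.3

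The direction is certain for any episode that worsens. The size is not, because no document gives w or v.

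**4. What the rate cannot show.** Suppose there are 200 injection-site reactions (hypothetical). The event rate is 100 × 200/1,738.6 = 11.5 per 100 patient-years in both cases below.
- 200 subjects once each: 200/420 = 48% of subjects. The first-event incidence rate lies between 11.5 (all events at the end of follow-up) and 200/(1,738.6 − 200 × 4.37) = 23.1 per 100 patient-years (all at the start).
- 20 subjects ten times each: 20/420 = 5%. The first-event incidence rate lies between 20/1,738.6 = 1.2 and 20/(1,738.6 − 20 × 4.37) = 1.2 per 100 patient-years.

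The subject count and the incidence rate separate the two cases; the event rate does not.

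**5. The documents side by side.** The once-per-subject rule in SAP 9.2 sits above both the Period 1 and the long-term sections, but it governs percentages. SAP 9.2.2 plans no percentages, so the rule has nothing to act on there. For long-term laboratory, liver and vital-sign findings in the same group, the SAP does plan the number and percentage of subjects (9.3.3.2, 9.3.3.3, 9.4.2). Adverse events are the exception.

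**The case against.** The case on the other side has real weight.

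- **A reader might infer that subject numbers are never reported.** The documents do not support that. Operations Manual 4.6 and Protocol 7.4 plan subject-level tables without limiting them to Week 24, and the SAP says that it elaborates the protocol. Period 1 has subject counts, and subjects with long-term serious or discontinuation events can be counted from the listings. What stands is narrower: SAP 9.2.2 does not specify the count.
- **A reader might put a size on the inflation by scaling the psoriasis rate in Protocol 2.2, 228.0 events per 100 patient-years.** That figure is already an event rate, and the documents do not say whether it includes worsening records. Scaling it could count the same effect twice.
- **A reader might conclude that records of one episode should be joined.** That could hide signals. The SAP defines a treatment-emergent event by onset after first dose and assigns long-term events to the treatment at the time. A separate record gives an event that began before dosing or on placebo, and worsened on risankizumab, its own on-treatment onset. Nor do the documents show a case report form link between a worsening record and the one before it.
- **Some key categories are less exposed.** Major cardiovascular events and adjudicated anaphylaxis come from adjudicated data. An event that passes through three grades adds only one severe record. The inflation falls mainly on overall and PT-level rates.
- **The analysis is descriptive.** It pools one group with no comparator or test, and SAP 9.1 says openly that subjects can contribute several events. So the event rate is a legitimate measure, but it is not enough alone.

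**Conclusion.** The point holds as a gap between the SAP and the Operations Manual. SAP 9.2.2 leaves out the planned number and percentage of subjects with treatment-emergent events. The rate that it gives instead counts a worsening episode more than once. With full follow-up of 420 subjects this concerns about 94% of some 1,739 patient-years on risankizumab; dropout would reduce the total and change the share. The size of the inflation is unknown, and the factors of 1.05 to 1.50 above are illustrations only. The loss of information about subjects does not depend on those assumptions. The primary efficacy conclusion is unaffected.

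**What to change.** In SAP 9.2.2.1, 9.2.2.2 and 9.2.2.4, add beside each event rate for the Any Risankizumab group:
- the number and percentage of subjects with at least one event, each counted once per PT and once per SOC, as Operations Manual 4.6 already plans;
- the exposure-adjusted incidence rate: subjects with a first event on risankizumab, divided by total time from first risankizumab dose to that first event or, without one, to the end of risk.

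Keep the event rate as SAP 9.1 defines it, with a footnote that a worsening recorded as a new event counts separately. Do not merge records, so that events that began before risankizumab and worsened on it stay visible.

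The cost is SAP wording, extra columns in tables already planned, and one time-to-first-event derivation. No new data collection is needed.
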